### 1.3 Benefit-Risk Statement

Risks associated with assignment to the placebo arm include adverse events (AEs) or worsening of symptoms. At this time, no data from pediatric PANS/PANDAS or OCD clinical trials suggest a risk of permanent worsening of symptoms or long-term outcome in children assigned to a placebo arm up to nine weeks' duration. The delay in access to active treatment is similar to what might be experienced by patients waiting for a clinician appointment and insurance authorization for treatment with IVIG in the community.

The risks of IVIG administration are well documented. In general, the incidence of AEs associated with IVIG tends to increase with the rate of infusions, and thus the recommended dosage, infusion rates, and monitoring procedures should be adhered to. Patients who are naïve to IVIG are more at risk than those who are well maintained and on regular therapy. In clinical studies with Panzyga, most ADRs observed in children were graded as mild, and many of them responded to simple measures, such as reduction of the infusion rate or temporary discontinuation of the infusion. With respect to the type of ADR, all were recognized for IVIG preparations. The most frequent ADR observed in the pediatric population was headache [22, 41].

The safety profile of IVIG is well characterized and, in general, the same type of adverse reactions may be expected for Panzyga. No new or unknown safety problems are expected to emerge, which are not already described in the Investigator's Brochure (IB) [22]. In general, adverse reactions such as headache, dizziness, vomiting, allergic reactions, chills, back pain, arthralgia, fever, low blood pressure and nausea may occasionally occur.

The safety profile of Panzyga is satisfactory and the number of ADRs are below the levels recommended by the US Food and Drug Administration (FDA) for products of this class. Efficacy and safety data with Panzyga are available from three clinical studies in 51 patients (including pediatric patients) with primary immunodeficiency and in 40 patients with immune thrombocytopenia [22].

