### 4.3.2 Premature Patient Withdrawal from Study Treatment

Patients may be withdrawn from study treatment for the following reasons:

- Occurrence of a condition or disease that interferes with the study treatment or represents an exclusion criterion.
- Administration of IVIG other than Panzyga. All patients who received at least one dose of the study treatment should be followed up per protocol until the study end without administration of the study product.

- Occurrence of an AE or SAE, which in the opinion of the investigator, precludes further treatment with study medication (Section 7.3.2).

If a patient shows worsening of their symptoms based on CGI-Improvement ratings, they will be presented to the site PI for review and treatment planning. Patients for whom worsening continues at a minimal level ("5" or "mildly worse") for an extended period of six weeks (2 visits) or moderately or greater level ("6" or "7"; much worse or very much worse) since last visit (up to three weeks) will be considered for premature withdrawal from the study drug and administration of appropriate standard of care treatment unless clinical interventions using approved study procedures and/or mediations have a reasonable likelihood to improve symptoms. Patients who experience an emergency worsening of symptoms may at the discretion of the site clinician be withdrawn from the study drug at any time to obtain necessary standard of care treatment. In addition, patients who develop exclusionary criteria (e.g. bipolar disorder, suicide attempt) will be withdrawn from the study drug and will receive appropriate standard of care treatment. All patients withdrawn from the study drug prematurely will be asked to continue the study as planned with modification of the study schedule (e.g. IMP administration and related to it safety lab tests will be omitted). Details of concomitant medications and procedures administrated per standard of care will be captured in patient case reports.

The eCRF will contain an End of Treatment and an End of Study page. The End of Treatment page will record whether the patient will be followed up per protocol, to allow for correct patient status tracking and to provide the reason for the drug withdrawal.

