### **7.3.2.2 Collection of AEs**

Adverse events will be collected throughout the study from the date of informed consent until the last study visit (end of study) and SAEs will be collected a further four weeks after last IMP dose if the site becomes aware of the event (no proactive monitoring).

The condition of the patient will be monitored throughout the study from the moment that informed consent has been given. During each visit, whether scheduled or unscheduled, AEs will be elicited using a standard non-leading question such as "How have you been since the last visit/during the previous study period?" Adverse events should be collected from the moment that informed consent has been given and at each subsequent visit.

Any AE or ADR which occurs during the study will be noted in detail in the appropriate pages of the eCRF. If the patient reports several signs or symptoms representing a single syndrome or diagnosis, the diagnosis should be recorded in the eCRF. The investigator will grade the severity of all AEs or ADRs (mild, moderate, or severe), the seriousness (non-serious or serious), and the causality as defined in Sections 7.3.2.3, 7.3.3, and 7.3.2.4. The Sponsor is responsible for assessing the expectedness of each ADR (expected or unexpected) as defined in Section 7.3.2.5.

In the event of clinically significant abnormal laboratory findings, the tests will be repeated as deemed necessary by the treating physician and the patient followed up until the laboratory values have returned to normal and/or an adequate explanation for the abnormality has become available.

Diseases, signs and symptoms, and/or laboratory abnormalities already present before informed consent will not be considered AEs unless an exacerbation in intensity or frequency (worsening) occurs.

Fluctuations of PANS/PANDAS symptoms will not be considered untoward medical occurrences and will not be reported as AEs if the investigator deems them to be within the expected range of normal symptom fluctuation or if they do not require concomitant medications or procedures.

The investigator will provide detailed information about any abnormalities and about the nature of and reasons for any action taken as well as any other observations or comments that may be useful for the interpretation and understanding of an AE or ADR.

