#### **7.3.3 Serious Adverse Events (SAEs)**

A **serious AE (SAE)** is any untoward medical occurrence that at any dose:

- results in death,
- is life-threatening (see below),
- requires hospitalization or prolongation of existing hospitalization,
- results in persistent or significant disability/incapacity,
- is a congenital anomaly/birth defect,
- is another important medical event.

**NOTE:** The term 'life-threatening' refers to an event in which the patient was, in the view of the reporting investigator, at immediate risk of death at the time of the event; it does not refer to an event which may hypothetically have caused death had it been more severe.

In deciding whether an AE/ADR is serious, medical judgment should be exercised. Thus, important AEs/ADRs that are not immediately life-threatening or do not result in death or hospitalization but may jeopardize the patient or may require intervention to prevent one of the other outcomes listed in the definitions above should also be considered serious.

In addition, although not classified under the seriousness criteria, all suspected transmissions of an infectious agent should be reported as SAE. A suspected virus transmission means that virus antigen has been detected in the patient. A passive transmission of antibodies alone does not constitute a suspected virus transmission.

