As discussed, for added safety monitoring, enrollment was be paused after the first █ patients have been randomized and enrolled in the study, for a planned IDMC review of unblinded safety and PK data, including IgG trough levels. Enrollment resumed only after IDMC data review of the first █ patients had been completed, and the IDMC had recommended to continue enrollment in the study. In addition, after █ patients have completed blinded treatment (Visit Week 9), an interim review of the preliminary safety and efficacy data will be conducted by IDMC. At this timepoint, the IDMC will independently evaluate all data accrued in this pivotal study to provide a statement on whether emerging data confirm the prospect of direct benefit and positive risk-benefit ratio for PANS patients treated with Panzyga. IDMC confirmation will justify the submission to concerned Health Authorities of the additional study protocol(s) evaluating other dose regimens of Panzyga treatment in patients with PANS. The actual numeric results will not be shared with the Sponsor or Investigators to ensure that bias will not affect subsequent study decisions since the data of the first █ patients will be included in the final statistical analysis. Details will be provided in the IDMC Charter.

In addition to the ongoing safety monitoring and periodic IDMC data review, study drug administration will be temporarily suspended, pending a safety investigation, in the event of an unacceptable increase in any AE the Panzyga group compared to the placebo group, with particular emphasis on TEEs and HTRs.

As specified by the EMA and the FDA, safety evaluation will include monitoring of short-term tolerance (blood pressure, heart rate, temperature, and monitoring of other AEs) at repeated intervals following IVIG infusion. All AEs that begin during or within 72 hours after an infusion will be classified and analyzed as infusional AEs. Adverse events will be evaluated with regard

to the infusion rates [57, 63]. The safety evaluation will also include a measure of suicidal ideation (C-SSRS), as recommended by the FDA for drug trials in patients with psychiatric symptoms [64].

A pre-treatment serum sample and one at the end of the study from each patient included in the clinical study will be stored at -70 °C for possible future testing [63].

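### The AE exemption for PANS symptom fluctuations needs only one of two conditions, so untreated worsening outside the expected range and treated fluctuations judged expected are absent from the AE tables

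*Protocol*

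**What the plan says.** - **The exemption (Protocol 7.3.2.2).** Fluctuations of PANS/PANDAS symptoms "will not be considered untoward medical occurrences and will not be reported as AEs" on either of two grounds. The first applies "if the investigator deems them to be within the expected range of normal symptom fluctuation". The second ground, sufficient by itself, reads "or if they do not require concomitant medications or procedures".
- **The general rule, one paragraph earlier in the same section.** Conditions already present before consent "will not be considered AEs unless an exacerbation in intensity or frequency (worsening) occurs".
- **Seriousness (Protocol 7.3.3).** An SAE "is any untoward medical occurrence that at any dose" meets one of the listed criteria. The waiver list at the end of Section 7.3.4 names three situations: hospital stays for the two-day infusions, elective or pre-planned surgery, and non-medical prolongation of a stay. PANS fluctuation is not among them.
- **Worsening as a recognised risk.** Section 1.3 states: "Risks associated with assignment to the placebo arm include adverse events (AEs) or worsening of symptoms". Under Section 4.3.2, patients with sustained or larger worsening on CGI-I "will be considered for premature withdrawal from the study drug and administration of appropriate standard of care treatment", subject to a stated exception. That section has the treatment recorded and provides an End of Treatment page for the reason. It does not say whether the worsening is entered as an AE.
- **Use of AE data.** Section 7.5 provides for temporary suspension "in the event of an unacceptable increase in any AE the Panzyga group compared to the placebo group", with emphasis on thromboembolic events (TEEs) and hemolytic transfusion reactions (HTRs). SAP Sections 11 and 11.1 build the safety analysis from reported AEs, laboratory results and physical findings. They name no separate table of PANS flares.

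**The concern.** An exemption for ordinary waxing and waning of the disease under study is reasonable. One would expect it to cover changes that are both unremarkable and in no need of intervention. This one applies when either is true, so it also covers changes that are remarkable, or that needed intervention.

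Children in one sequence move from active treatment to blinded placebo without a wash-out, and those in the other spend the first nine weeks on placebo. Worsening of behaviour is therefore a safety question in its own right. If part of it is filtered out before it becomes an AE, the AE tables understate it. The filter also depends on investigator judgement and on the decision to treat, and either could differ between arms even under blinding.

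**Working it through.** There is no stated figure to reproduce. The check is one of logic, followed by a comparison of the provisions.

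**1. What the exemption covers.** Let A mean that the investigator judges the fluctuation within the expected range. Let B mean that no concomitant medication or procedure is required.

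- As written: exempt = A or B, so reported = (not A) and (not B).
- With *and*: exempt = A and B, so reported = (not A) or (not B).

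| Fluctuation | A | B | As written | With *and* |
|---|---|---|---|---|
| Within range, untreated | yes | yes | exempt | exempt |
| Within range, treated | yes | no | exempt | reported |
| Outside range, untreated | no | yes | exempt | reported |
| Outside range, treated | no | no | reported | reported |

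As written, 1 of 4 combinations is reported; with *and*, 3 of 4 are. The two middle rows are the issue. These are counts of logical cases, not of events.

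**2. Against the preceding paragraph.** The general rule turns on whether a pre-existing symptom has worsened; treatment plays no part. An untreated worsening outside the expected range is an AE under that paragraph and exempt under the later one. Severity grading in Section 7.3.2.3 does not depend on treatment either: it rests on interference with routine activities. An incapacitating but unmedicated episode would be graded severe if reported, yet the exemption means it need not be.

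**3. Against the SAE definition.** Section 7.3.2.2 says that exempt fluctuations are not untoward medical occurrences, and Section 7.3.3 makes that term the entry condition for an SAE. Read literally, an exempt fluctuation cannot be an SAE whatever its consequences. The waiver list does not include such events, and Section 7.3.3 calls for medical judgement on seriousness. The sections therefore point in different directions.

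**4. Against the withdrawal provision.** Worsening that leads to study drug being stopped is not stated to be an AE, and Section 7.3.2.2 does not say whether stopping study drug counts as a procedure. Whether such a case reaches the SAP count of AEs leading to withdrawal depends on how the investigator reads the exemption.

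**5. What other records hold.** CGI-I, the C-SSRS, concomitant-medication records and the End of Treatment reason all carry information on worsening. SAP Section 4.1 places CY-BOCS every three weeks in the first phase and at Week 18. On that schedule, an episode that arises and resolves between Weeks 9 and 18 may leave no CY-BOCS trace.

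**The case against.** The other side has several good points.

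- **Not all flares are lost.** A reader might infer that any flare outside the normal range, or any treated flare, can vanish from the safety data. The documents do not support that. A flare that is both is still reported, and the records listed above retain traces of the rest. What is lost is entry in the AE tables, for two sub-cases.
- **Safety suspension is not shown to be compromised.** A reader might also infer that the exemption undermines the committee's suspension rules. The only quantified rule (Protocol 6.2.2) concerns venous TEEs and acute renal failure, which the exemption does not touch. The broader provision in Section 7.5 stresses TEEs and HTRs, and at the interim review the committee evaluates all accrued data, not AE counts alone.
- **Loss of SAEs is possible, not demonstrated.** The literal wording reaches SAEs, but the waiver list suggests this was not intended. It is an ambiguity to close.
- **General rule and exception.** The two paragraphs could be read as a general rule with a disease-specific exception, fluctuation being something milder than worsening. This helps only partly. Fluctuation is undefined, and if it meant normal variation alone, the condition about the expected range would be redundant.
- **Worsening after crossover is partly covered.** The first secondary endpoint compares CY-BOCS at Weeks 9 and 18 in the Panzyga–Placebo sequence. That is a group mean at one later time point and does not replace event capture.
- **The treated-but-expected case may be rare.** Section 4.2.2 forbids or restricts most relevant treatments. That may be so, but the same restrictions make the untreated, outside-range case more plausible.
- **Unseen text.** Sections 6.1, 7.3.1 and 9.2.3 and the flow charts are redacted or blank in this copy, and the committee charter was not supplied. Separate flare capture there cannot be excluded, though it would not reconcile the two paragraphs of Section 7.3.2.2.

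**Conclusion.** The point holds as a defect of wording with a limited reach. Two kinds of event are absent from the AE tables as the rule stands: worsening outside the expected range that is untreated, and treated fluctuation judged within range. Both could also escape SAE assessment. The rule conflicts with the paragraph before it, and the two need reconciling.

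The size is two of four logical cases. The number of events cannot be computed because the documents give no flare rate, and the direction of any effect on the comparison of arms is unknown. The primary efficacy analysis does not depend on this rule.

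The conclusion assumes that *or* is applied literally and that no redacted section narrows the exemption. It is a worthwhile, inexpensive improvement to safety capture, not evidence that the safety data would be unreliable.

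**What to change.** Amend Section 7.3.2.2 in two places:

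1. Replace *or* with *and*, so that a fluctuation is exempt only if it is within the expected range and also needs no concomitant medication or procedure.
2. Add one sentence: any fluctuation that meets a seriousness criterion in Section 7.3.3 is reported as an SAE regardless of the exemption.

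This changes what is reported, not how patients are treated, and still leaves ordinary untreated fluctuation out of the AE data.

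The cost is one word and one sentence in an amendment, plus more AE entries. Some of those entries will reflect lack of efficacy: if Panzyga works, untreated worsening may accumulate in the placebo column and mix efficacy with safety. Tabulating PANS-symptom AEs separately from other AEs, with a line in SAP Section 11.1, deals with that. Events before and after the change would be collected under different rules, so the report should state the date it took effect.

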### **7.3.2.3 Severity of AEs**

The intensity/severity of AEs will be graded as follows:

- **Mild:** an AE, usually transient, which causes discomfort but does not interfere with the patient's routine activities

- **Moderate:** an AE which is sufficiently discomforting to interfere with the patient's routine activities
- **Severe:** an AE which is incapacitating and prevents the pursuit of the patient's routine activities

The grading of an AE is up to the medical judgment of the investigator and will be decided on a case-by-case basis.

#### **7.3.2.4 Causality of AEs**

The relationship of AEs to the administered IMP will be assessed by the investigator:

- **Probable:** reports including good reasons and sufficient documentation to assume a causal relationship, in the sense of plausible, conceivable, likely, but not necessarily highly probable. A reaction that follows a reasonable temporal sequence from administration of the IMP; or that follows a known or expected response pattern to the suspected medicine; or that is confirmed by stopping or reducing the dosage of the medicine and that could not reasonably be explained by known characteristics of the patient's clinical state.
- **Possible:** reports containing sufficient information to accept the possibility of a causal relationship, in the sense of not impossible and not unlikely, although the connection is uncertain or doubtful, for example because of missing data or insufficient evidence. A reaction that follows a reasonable temporal sequence from administration of the IMP; that follows a known or expected response pattern to the suspected medicine; but that could readily have been produced by a number of other factors.
- **Unlikely:** reports not following a reasonable temporal sequence from IMP administration. An event which may have been produced by the patient's clinical state or by environmental factors or other therapies administered.
- **Not related (unrelated):** events for which sufficient information exists to conclude that the etiology is unrelated to the IMP.

#### **7.3.2.5 Classification of ADRs by Expectedness**

ADRs will be classified by the Sponsor as either expected or unexpected:

- **Expected:** an ADR that is listed in the current edition of the IB.
- **Unexpected:** an ADR that is not listed in the current edition of the IB, or that differs because of greater severity or greater specificity.

#### **7.3.2.6 Outcome of AEs**

The outcome of all reported AEs has to be documented as follows:

1. Recovered, resolved
2. Recovering, resolving
3. Not recovered, not resolved
4. Recovered, resolved with sequelae

5. Fatal
6. Unknown

**NOTE:** A patient's **death** per se is not an event, but an outcome. The event which resulted in the patient's death must be fully documented and reported, even in case the death occurs within four weeks after IMP treatment end and regardless of whether or not it is considered treatment-related.

#### **7.3.2.7 Action(s) taken**

AEs requiring action or therapy must be treated with recognized standards of medical care to protect the health and well-being of the patient. Appropriate resuscitation equipment and medicines must be available to ensure the best possible treatment in an emergency situation.

The action taken by the investigator must be documented:

##### ***General actions taken in the event of an AE***

- None
- Medication (other than IMP) or other (e.g., physical) therapy started
- Test performed
- Other (to be specified)

##### ***IMP-related actions taken in the event of an AE***

- Dose Not Changed
- Dose Reduced
- Drug Interrupted
- Drug Withdrawn
- Not Applicable
- Unknown

The investigator will follow up on each AE until it has resolved or until the medical condition of the patient has stabilized. Any relevant follow-up information will be reported to the Sponsor.

#### **7.3.3 Serious Adverse Events (SAEs)**

A **serious AE (SAE)** is any untoward medical occurrence that at any dose:

- results in death,
- is life-threatening (see below),
- requires hospitalization or prolongation of existing hospitalization,
- results in persistent or significant disability/incapacity,
- is a congenital anomaly/birth defect,
- is another important medical event.

**NOTE:** The term 'life-threatening' refers to an event in which the patient was, in the view of the reporting investigator, at immediate risk of death at the time of the event; it does not refer to an event which may hypothetically have caused death had it been more severe.

In deciding whether an AE/ADR is serious, medical judgment should be exercised. Thus, important AEs/ADRs that are not immediately life-threatening or do not result in death or hospitalization but may jeopardize the patient or may require intervention to prevent one of the other outcomes listed in the definitions above should also be considered serious.

In addition, although not classified under the seriousness criteria, all suspected transmissions of an infectious agent should be reported as SAE. A suspected virus transmission means that virus antigen has been detected in the patient. A passive transmission of antibodies alone does not constitute a suspected virus transmission.

